3.2. Subject Restrictions

Lifestyle/ Dietary

None

Medications and Treatments

During the entire study (screening – end of study):

- A. Subjects are not permitted use of any medication other than the allocated study treatment and medications to treat chronic, controlled diseases (see Section 4.2, Number 3 for details). In addition, subjects should also refrain from non-drug concomitant treatment or procedures that may interfere with study treatment. In case subjects use any concomitant medication that could interfere with the interpretation of the study results, they will be discontinued from the study.
- B. Intranasal sprays including saline or decongestants within 24 hours.
- C. Intranasal steroids within the past 14 days.
- D. Expectorants, mucolytics, or antitussives within the past 12 hours.
- E. Cough/throat lozenges, menthol chest rub, menthol vaporizers or honey within 6 hours.

Document Name	CCI	Protocol B_Final_Amendment 4_Clean_QA Review		
Type	Version	Document Identifier	Effective Date	
elido_clinical_doc	1.0; CURRENT; Most-Recent; Effective	090032d580d43d4b	19-May-2017 09:57:58	
Reason For Issue	Auto Issue			

F. Non-steroidal anti-inflammatory drug (NSAID), or acetyl salicylic acid within the past 12 hours (immediate release) and 24 hours (sustained release). Acetaminophen/paracetamol may be used occasionally for fever or headache, but subjects should be instructed to try to avoid use if possible.

G. Oral decongestants within 12 hours for short-acting and 24 hours for long-acting.

H. Long acting antihistamines (cetirizine, fexofenadine, hydroxyzine, and loratadine) within 5 days.

I. Short acting antihistamines (e.g., chlorpheniramine, brompheniramine, diphenhydramine), clemastine, long acting forms of chlorpheniramine within 2 days.

J. Asthma medications with the exception of beta-agonists. Subject should be on a stable dose (≥ 7 days) within 24 hours.

K. Herbal OTC medicines for cough/cold (e.g., echinacea, garlic supplements, etc.) for 24 hours.

L. Systemic corticosteroids, immunomodulators within 3 months.

M. Antibiotics within the past 14 days.

N. A flu shot within the past 48 hours.

O. Use of Tamiflu[®] (oseltamivir) or Relenza[®] (zanamivir) within the last 7 days.

P. Other investigational drugs or devices.

Q. Any other treatment the Investigator deems unacceptable for this study.

3.3. Type and Planned Number of Subjects

A SUFFICIENT NUMBER OF SUBJECTS WILL BE SCREENED IN ORDER TO ENROLL approximately 300~~170~~ male and female subjects (all sites will be instructed to enroll approximately equal numbers of males and females) ~~will be randomized to ensure 274 subjects (137 subjects per treatment arm) complete the study.~~ Eligible subjects will be aged 18 to 75 years, in good general health and experiencing symptomatic common cold symptoms for ~~≤48~~ 72 hours.

Symptomatic common cold is defined as:

- TSS ≥ 9 (baseline sum of the 8 common cold symptoms described in Section 6.1.7.) AND

Document Name	CCI	Protocol B_Final_Amendment 4_Clean_QA Review		
Type	Version	Document Identifier	Effective Date	
elido_clinical_doc	1.0; CURRENT; Most-Recent; Effective	090032d580d43d4b	19-May-2017 09:57:58	
Reason For Issue	Auto Issue			

- Score ≥ 1 for at least one of the following symptoms: sore throat, runny nose, or blocked nose.

To participate, each subject must meet all study Inclusion and none of the Exclusion criteria at Screening/Baseline visit (Visit 1) prior to randomization. See Section 4.1. and 4.2. for details on Inclusion and Exclusion criteria.

3.4. Study Design and Dose Justification

The target population is symptomatic subjects with the common cold. These subjects are studied in the outpatient setting and efficacy is monitored by the subjects' evaluations of specific symptoms. Safety is evaluated by subject reported adverse events.

While common cold symptoms manifest for 7-10 days, the most severe symptoms typically present within the first 4 days of symptom onset, thus the primary endpoint will focus on nasal symptoms score on Days 1 through 4.

Intranasally administered 1146A formulation containing carbomer 980 (Carbopol® 980) stabilized with buffers will be compared to placebo. The individual components of 1146A are used as excipients in pharmaceutical and cosmetic preparations. The safety of carbomers was assessed by American College of Toxicology in 1982 and reevaluated in 2002; the conclusion was that carbomers are safe for use in humans [ACT, 1982; ACT, 2002].

Tolerability and safety of the intranasal formulation has been demonstrated in rats, but no published literature was found on CCI carbomer 980 administered intranasally and used four times daily over 7 days. CCI

[REDACTED]

The concentration of carbomer selected is based on *in vitro* data (CCI carbomer 980), which has demonstrated the ability to entrap common cold viruses. The rationale for the dose and regimen is to maximize the coverage of the nasal epithelium commensurate with consumer acceptability. The maximum frequency of use and volume of application are based on the regimen for competitive products (Vick's First Defense is 2-3 sprays 4 times daily approximately 4 hours apart) [Vicks First Defence Nasal Spray, 2014].

Document Name	CCI	Protocol B_Final_Amendment 4_Clean_QA Review		
Type	Version	Document Identifier	Effective Date	
elido_clinical_doc	1.0; CURRENT; Most-Recent; Effective	090032d580d43d4b	19-May-2017 09:57:58	
Reason For Issue	Auto Issue			

4. SELECTION OF STUDY POPULATION AND WITHDRAWAL CRITERIA

Specific information regarding warnings, precautions, contraindications, adverse events, and other pertinent information on the GSK investigational product or other study treatment that may impact subject eligibility is provided in the Investigator Brochure (IB).

Deviations from inclusion and exclusion criteria are not allowed because they can potentially jeopardize the scientific integrity of the study, regulatory acceptability or subject safety. Therefore, adherence to the criteria as specified in the protocol is essential.

4.1. Inclusion Criteria

A subject will be eligible for inclusion in this study only if all of the following criteria apply:

1. CONSENT

Demonstrates understanding of the study procedures, restrictions and willingness to participate as evidenced by voluntary written informed consent and has received a signed and dated copy of the informed consent form.

2. AGE

Aged between 18 to 75 years inclusive.

3. GENDER

Male or female.

4. GENERAL HEALTH

Good general and mental health with, in the opinion of the Investigator or medically qualified designee no clinically significant and relevant abnormalities in medical history or upon physical and Investigator-led nasal examination.

5. CONTRACEPTION

Females of childbearing potential (refer to Section 4.4.) who are, in the opinion of the Investigator, practicing a reliable method of contraception. Adequate contraception is defined as abstinence, oral contraceptive, either combined or progestogen alone OR

Document Name	CCI	Protocol B_Final_Amendment 4_Clean_QA Review		
Type	Version	Document Identifier	Effective Date	
elido_clinical_doc	1.0; CURRENT; Most-Recent; Effective	090032d580d43d4b	19-May-2017 09:57:58	
Reason For Issue	Auto Issue			

injectable progestogen OR implants of levonorgestrel OR estrogenic vaginal ring OR percutaneous contraceptive patches OR intrauterine device or intrauterine system OR double barrier method (condom or occlusive cap [diaphragm or cervical vault caps] plus spermicidal agent [foam, gel, film, cream, suppository]) OR male partner sterilization prior to the female subject's entry into the study, and this male is the sole partner for that subject.

6. STUDY SPECIFIC

Investigator confirmed diagnosis of symptomatic common cold with an onset of ≤ 48 hours prior to randomization. Symptomatic common cold is defined as TSS ≥ 9 AND a score ≥ 1 for at least one of the following symptoms: sore throat, runny nose, or blocked nose.

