Details of amendments to the protocols should be recorded on the following page. Protocol modifications must be prepared by a representative of GSKCH. All changes must be justified in the Reason for Amendment section of the following Protocol Amendment Page. Approval of amendments will be made by the original protocol signatories or their appropriate designees.

All major/substantial protocol modifications must be reviewed and approved by the appropriate IRB in accordance with local requirements, before the revised edition can be implemented.

All non-substantial/ minor/ administrative amendments should be submitted to the IRB as per country specific requirements. In some countries pre-approval of a minor amendment is not required and will just be held on file by the sponsor and Investigator.

 GlaxoSmithKline	Document Name	CCI	Protocol B	Final	Amendment 4	Clean	QA Review
	Type	Version				Document Identifier	Effective Date
	elde_clinical_doc	1.0	CURRENT	Most Recent	Effective	090032d580d43d4b	19 May 2017 09:57:58
	Reason For Issue	Auto Issue					

PROTOCOL AMENDMENT PAGE

Details of all amendments should be recorded in the table below. Affected sections should be listed in the table; the actual amendment/ change should be made in the relevant section of the main protocol.

To highlight the change, the following features will be used:

To add text: Use of **CAPITAL LETTERS, BOLD AND UNDERLINE**

To delete text: Use of Strikethrough e.g. ~~strikethrough~~

Amendment No. & New Protocol Version No.	Type of Amendment	Reason for Amendment	Other Documents Requiring Amendment	Section(s) Amended	PI Amendment Agreement Signature & Date
Amendment No.: 1	Non-Substantial/Minor 	During application, the device should be held between the index and middle fingers, not the index and ring fingers.	Informed Consent  Yes  No Safety Statement  Yes  No CRF  Yes  No	Appendix 2- Subject Instructions for Use, Step 5; Section 5.2.1.	Signature: PPD 
Protocol Version No.: 1.0.2.0	Substantial/ Major 				Date: PPD 

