Amendment No.: 2	Non-Substantial/Minor 	The head should be tilted forward slightly when inserting the nasal applicator into the nostril.	Informed Consent  Yes  No Safety Statement  Yes  No CRF  Yes  No	Appendix 2- Subject Instructions for Use, Step 5; Section 5.2.1.	Signature: PPD 
Protocol Version No.: 2.0.3.0	Substantial/ Major 				Date: PPD 

 GlaxoSmithKline	Document Name	CCI	Protocol B	Final	Amendment 4	Clean	QA Review
	Type	Version				Document Identifier	Effective Date
	elde_clinical_doc	1.0: CURRENT: Most-Recent: Effective				090032d580d43d4b	19 May 2017 09:57:58
	Reason For Issue	Auto Issue					

Amendment No. & New Protocol Version No.	Type of Amendment	Reason for Amendment	Other Documents Requiring Amendment	Section(s) Amended	PI Amendment Agreement Signature & Date
Amendment No.: 3.0	Non-Substantial/Minor 	1. The eligibility criteria for common cold symptom onset was changed from 48 hours to 72 hours 2. A recent history of alcohol or other substance abuse within the past 5 years was changed to 1 year 3. Clarified how urine drug screen results would be documented in the CRF 4. Additional wording included regarding the statistical impact of subjects with common cold between >48 and \leq 72 hours and that it might be reviewed 5. Date and time of symptom onset will be captured in the CRF	Informed Consent  Yes  No Safety Statement  Yes  No CRF  Yes  No	1. Schedule of Events, Protocol Synopsis, Section 3.1 Study Design, Section 3.3 Type and Planned Number of Subjects, Section 4.1 Inclusion Criteria-6, Section 6.1.7 Self-Assessment of Common Cold Signs & Symptoms by Subjects 2. Section 4.2. Exclusion criteria-6A 3. Section 6.1.9 Urine Drug Screening Test 4. Protocol Synopsis, 9.3.2 Primary Analysis 5. Section 6.1.7 Self-	Signature: PPD Date: PPD
Protocol Version No.:4.0	Substantial/ Major 				

 GlaxoSmithKline	Document Name	CCI	Protocol B	Final	Amendment 4	Clean	QA Review
	Type	Version				Document Identifier	Effective Date

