6.1.7. Self-Assessment of Common Cold Signs & Symptoms by Subjects

Common cold signs and symptoms will be self-evaluated by the subject at Screening before the first dosing and will be documented in the source document and recorded in the CRF.

In order to qualify each subject for eligibility, the Investigator will verbally confirm with the subject that the onset of any common cold symptoms occurred within 48 72 hours of randomization. **THE DATE AND TIME OF SYMPTOM ONSET WILL BE CAPTURED IN THE CRF.** The investigator will also ensure that the subject has a symptomatic common cold, which is defined as TSS ≥ 9 (baseline sum of the 8 common cold symptoms described below), AND a score ≥ 1 for at least one of the following symptoms: sore throat, runny nose, or blocked nose.

The following are the symptoms of common cold and their severity grading:

Nasal symptoms:

- runny nose
- blocked nose
- sneezing

Other symptoms

- headache
- muscle ache
- chills
- sore throat
- cough

Document Name	CCI	Protocol B_Final_Amendment 4_Clean_QA Review		
Type	Version	Document Identifier	Effective Date	
elido_clinical_doc	1.0; CURRENT; Most-Recent; Effective	090032d580d43d4b	19-May-2017 09:57:58	
Reason For Issue	Auto Issue			

Each individual sign/symptom will be scored using the following 4 point scale:

- 0 = absent symptoms (no sign/symptom evident)
- 1 = mild symptoms (sign/symptom clearly present, but minimal awareness; easily tolerated)
- 2 = moderate symptoms (definite awareness of sign/symptom that is bothersome but tolerable)
- 3 = severe symptoms (sign/symptom that is hard to tolerate; causes interference with activities of daily living and/or sleeping)

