3.1. Overall Study Design and Plan

This is a multi-center, randomized, parallel-group, double blind, 2-group, placebo-controlled study to evaluate the efficacy and safety of 1146A formulation CCI carbomer 980 gel nasal spray) in adult subjects with symptomatic common cold in an outpatient setting.

At Screening (Day 1, Visit 1), subjects with symptoms consistent with symptomatic common cold of a \leq 72 hour duration will provide written informed consent to be enrolled into the study. During this visit, subjects will undergo eligibility screening, which includes: assessment of common cold symptoms and diagnosis by the Investigator; review of demographics, medical and medication history; vital sign assessments (blood pressure, pulse rate, respiratory rate, oral body temperature, height and weight measurements); physical examination; Investigator-led nasal examination; urine pregnancy test (only female subjects of childbearing potential); and urine drug screen.

Eight common cold symptoms are defined as follows:

Nasal symptoms:

- runny nose
- blocked nose
- sneezing

Other symptoms

- headache
- muscle ache
- chills
- sore throat
- cough

Each individual sign/symptom will be scored using the following 4 point scale:

0 = absent symptoms (no sign/symptom evident)

1 = mild symptoms (sign/symptom clearly present, but minimal awareness; easily tolerated)

2 = moderate symptoms (definite awareness of sign/symptom that is bothersome but tolerable)

3 = severe symptoms (sign/symptom that is hard to tolerate; causes interference with activities of daily living and/or sleeping)

Only subjects meeting all eligibility criteria including the following symptomatic common cold symptoms will be enrolled into the study:

1. A confirmed common cold diagnosis with symptoms \leq 72 hours;
2. Total Symptom Score (TSS) \geq 9 (baseline sum of the 8 common cold symptoms);
3. Score \geq 1 for at least one of the following symptoms: sore throat, runny nose, or blocked nose.

Approximately 170 eligible subjects will be stratified and randomized to treatment with 1146A nasal spray or placebo (vehicle, nasal spray) in a 1:1 ratio at multiple sites. All sites should make an effort to enroll approximately equal number of males and females into the study. The study sites will stratify and randomize qualified subjects using Interactive Response Technology (IRT).

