Urine pregnancy testing not completed	Significant
Subject who misses 2 or more of their nasal symptom assessments on any day during Days 1-7	Not Significant
Any subject who misses a total of 6 or more of their nasal symptom assessments during Days 1-7	Not Significant
Subject who misses 2 or more of their nasal symptom assessments on any day during Days 1-4	Significant
Any subject who misses a total of 4 or more of their nasal symptom assessments during Days 1-4	Significant
Screening procedures not completed	Significant
Subject not enrolled within 72 hours of symptom onset	Significant
Subject randomized out of sequence (IWRS problem)	Significant
Received incorrect treatment, not according to randomization schedule	Significant
Subject randomized prior to the completion of ICF	Significant
SAE not reported by site to PPD at all or not within 24 hours of awareness	Significant
SAE not reported by PPD to GSKCH at all or not within 1 business day of awareness	Significant
Pregnancy not reported by site to PPD within 2 weeks of learning of subject becoming pregnant	Significant
Site did not follow up to obtain required information for SAE reporting	Significant
AE not included on AE section of the eCRF	Not Significant
Failure to discontinue subjects that meet defined discontinuation criteria	Significant
Subject did not sign ICF	Significant
ICF signed by subject prior to IRB approval	Significant
ICF signed by subject but not approved by IRB	Significant
Original ICF signed and dated after screen/enroll date	Significant
ICF was lost, no copy available	Significant
ICF was lost, copy available	Significant
Subject signed consent but did not date it, but there is other sufficient information to confirm the date	Significant
Subject forgot to sign the ICF but gave verbal consent	Significant
Investigator and/or witness did not sign or date the ICF and there isn't any supporting documentation to confirm that the consent process was performed appropriately	Significant
Version date not recorded on ICF	Significant
Subject signed a superseded/updated version of the ICF (and never signed correct version)	Significant

[figure not shown]
DESCRIPTION OF RULE	SIGNIFICANCE
Revised ICF not signed; subject visit has occurred & not remediated at a subsequent visit	Significant
Blood Pressure Repeat Assessments not completed in 1-2 minute intervals per protocol.	Significant
Early Termination procedures not completed	Significant

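### Inclusion criterion 6 in protocol Section 4.1 prints a 48-hour onset limit with no 72, while every other statement of the limit includes 72; check the source page and reconcile.

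*Protocol*

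**What the plan says.** Protocol Section 4.1 makes a subject eligible only when all of its listed criteria are met. Criterion 6 calls for an "Investigator confirmed diagnosis of symptomatic common cold with an onset of ≤ 48 hours prior to randomization". No 72 appears there in the text as supplied. Section 4 adds: "Deviations from inclusion and exclusion criteria are not allowed".

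The Protocol Amendment Page records under Amendment 3: "The eligibility criteria for common cold symptom onset was changed from 48 hours to 72 hours". Its list of amended sections includes "Section 4.1 Inclusion Criteria-6". The same page explains that deleted text stays on the page, struck through, beside the new text.

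Elsewhere the limit carries 72. Section 6.1.7 has the investigator confirm that "onset of any common cold symptoms occurred within 48 72 hours of randomization". SAP Section 3.1 gives "A confirmed common cold diagnosis with symptoms \leq 72 hours" as an enrolment condition, and SAP Appendix C lists as a significant deviation "Subject not enrolled within 72 hours of symptom onset". Protocol 9.3.2 and SAP 8.1.1 provide for a review or an adjusted analysis if more than 10% of the relevant subjects entered beyond 48 hours.

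**The concern.** Section 4.1 decides who may be randomized. If it limits onset to 48 hours while 6.1.7 and the SAP work to 72, a subject between the two limits is classified in opposite ways depending on the section consulted. A site that checks the criteria list refuses entry; a site that follows 6.1.7 enrols.

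Once such a subject is enrolled, three further steps depend on the limit applied:

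- **Withdrawal.** Section 4.5 lists failure to meet study criteria among the circumstances requiring discontinuation of treatment and/or withdrawal. Under Section 3.1 such subjects have end-of-study assessments and are discharged. Section 9.2.5 does not impute data after dropout in the primary analysis.
- **Per-protocol population.** SAP 4.4.4 sends violators of eligibility criteria to case-by-case review. Who goes to review depends on the limit.
- **Deviation reporting.** SAP Appendix C tests onset at 72 hours only.

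The modified ITT definition does not exclude eligibility violators. The primary analysis would therefore be affected through who enters and who is withdrawn, not through a direct exclusion.

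**Working it through.** No power, variance or sample-size figure is involved. The check sets the statements of the limit side by side and asks whether a reading loss explains the odd one out.

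**1. Statements of the onset limit, as supplied**

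| Place | Limit shown |
|---|---|
| Protocol 4.1, criterion 6 | ≤ 48 only |
| Protocol schedule of events, footnote b | 48 and 72 side by side |
| Protocol synopsis (design, enrolment criteria, Visit 1 list, planned number, main criteria) | 48 and 72 side by side |
| Protocol 3.1 | 48 and 72 side by side |
| Protocol 3.3 | 48 struck through, then 72 |
| Protocol 6.1.7 | 48 and 72 side by side |
| SAP 3.1 | ≤ 72 |
| SAP Appendix A, footnote b | 48-72 |
| SAP Appendix C (two entries) | 72 |

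Section 3.3, where the strikethrough survived, shows how to read the side-by-side entries: 48 deleted, 72 current. The Amendment 3 record and the planned analysis of the > 48 to 72 hour subset agree. Criterion 6 is the only statement showing 48 without 72.

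**2. Could the 72 have been lost in reading the PDF?** In the other tracked edits checked, the strikethrough or the old value is what was damaged, and the new text survived:

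- Onset limit: 72 is present in every other protocol statement.
- Sample size (synopsis, 3.1): the old and new numbers run together as 300170, and the new 170 is there.
- Section 5.2.1: the new word MIDDLE is there.
- Section 6.2.3: the added words OR BELOW are there.
- Exclusion 6A, logged as 5 years changed to 1 year: the old value appears as a stray ≤ sign, and the new 1 is there.

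If criterion 6 is a reading loss, it is the only edit among these where the new value vanished and the old one stayed clean. That leans towards an edit not made on the page but does not prove it.

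**3. Is there another change not carried through?** Protocol 5.8.1 caps sites at 45, stated as 15% of the target. 0.15 × 300 = 45, whereas 0.15 × 170 = 25.5, and SAP 4.3 gives 26. So at least one number was left behind by an amendment. The parallel is imperfect: Amendment 4 does not list 5.8.1 as amended, while Amendment 3 does list criterion 6.

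**4. One subject traced through the text as printed.** Take onset 60 hours before randomization. Criterion 6: 60 > 48, not met. The 72-hour window in 6.1.7: 60 < 72, met. SAP Appendix C onset entries: 60 < 72, no deviation. The two documents give opposite classifications.

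**The case against.** The strongest objection is that this is a reading artefact. Amendment 3 names this very criterion as changed to 72 hours, the file keeps deleted text on the page, and mark-up was handled badly in several places. A struck-through 48 with a dropped 72 would look exactly like what we have, and would not be an error in the plan. This stands as far as it goes: the supplied text cannot rule it out. It does not dispose of the point, because the amendment log shows what was intended rather than what the page prints, and the other edits checked kept their new text.

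A second objection is that the intended window is clear from everything else, including the analysis plan, and that Amendment 3 also called for changes to the consent form and the CRF. That makes divergent practice between sites less likely. It does not remove the need for the governing list to agree.

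A reader might also infer that 18 or more subjects are affected, since 10% of 170 is 17. The documents do not support that count. The 10% is a trigger for an additional analysis, not an expected share, and SAP 8.1.1 applies it to modified ITT subjects enrolled after Amendment 3, not to all 170.

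**Conclusion.** The contradiction stands on the text as supplied: the governing criterion prints 48 hours and every other statement of the limit includes 72. It affects every subject with onset more than 48 and up to 72 hours before randomization. Their number is not given, and no defensible estimate follows from the documents.

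The conclusion assumes that the source page reads as the supplied text does. Two stronger readings go too far. One is that the operative criterion has been shown to remain at 48 hours; a lost 72 is possible. The other is that such a subject is plainly eligible everywhere else; most other protocol entries print both numbers, and they read as 72 only once lost strikethrough is allowed for. Nor do the documents show that any subject was refused or withdrawn on this ground.

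The boundary sign is a secondary matter. The protocol synopsis, protocol 9.3.2 and one SAP Appendix C entry show < 72; SAP 8.1.1 shows ≤ 72. The same Appendix C table prints > 9 and > 1 where the protocol has ≥ 9 and ≥ 1, so the equality bars may simply have been lost. It is something to confirm, not a finding.

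**What to change.** 1. Check criterion 6 of protocol Section 4.1 on the source page. If it shows 48 struck through with 72 beside it, nothing further is needed on the main point.
2. If it prints only 48, bring it into line with the 72-hour window adopted by Amendment 3 and used in 6.1.7 and the SAP.
3. In that case also reconcile protocol Sections 4.1, 4.5 and 6.1.7 and SAP Appendix C, so that a subject with onset > 48 to 72 hours is classified the same way throughout.
4. While doing so, confirm whether the boundary is < 72 or ≤ 72 in the protocol synopsis, protocol 9.3.2, SAP 8.1.1 and SAP Appendix C.

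The cost is one number in the criteria list, possibly a comparison sign, and a consistency read. No change to the design or the analysis is needed, because the wider window is already the documented intention.
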